Cohort study with pre and post assessments around an intervention.

Setting/Participants:

Clinicians at CHOP and parents of children previously hospitalized in the ICU will be invited to participate in the co-design portion of the study. A separate group of volunteer attending intensivists, cardiologists, cardiac surgeons, front line clinicians, nurses, and social workers from the pediatric CICU at the Children's Hospital of Philadelphia (CHOP) will undergo the CST program intervention and participate in observed family meetings. Other clinicians who are participating in an observed family meeting will also be enrolled. Parents or legal guardians and their children in the CICU who have been there for at least 7 days and are expected to stay at least another 7 days will also be consented and enrolled.

Study Interventions and Measures:

Intervention:

The intervention is a CST for a group of interprofessional clinicians that will include practice in communication skills of giving bad news and eliciting goals of care and building team collaboration. Parental-facing aspects of the intervention include parental preparation

for family meetings and provision of written summary of the family meeting after its completion.

Measures:

The Co-design process to develop the intervention will have focus groups to evaluate the interventions' content and feasibility and a survey to measure participant engagement in the focus groups.

The impact of the CST program on CICU clinicians' perceived usefulness and satisfaction with the training will be measured with a post-CST survey. This survey will also measure clinician burnout, demographics and experience with modalities of communication pre and during the COVID-19 pandemic. Furthermore, a random sample of 8 clinicians participating in the CST will complete an acceptability interview regarding their thoughts on the intervention.

For the actual family meetings, assessment of the impact of the CST on communication and team function in actual family meetings pre and post-CST will be done by coding audio recordings using the same tools as in simulated encounters and qualitative coding of content. Collaboration will be measured using the amount of time different members of different disciplines speak, and team member perception and satisfaction with collaboration will be measured using a validated tool.

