2.2 Secondary Objectives (or Aim)

The secondary objectives are to:

- Evaluate CICU clinicians' perceived feasibility and acceptability with the CST
- Evaluate CST impact on communication skills and team function in the actual family meeting
- Evaluate clinicians' burnout rates and changes that CICU clinicians have implemented regarding family meetings due to the 2020 COVID-19 pandemic
- Evaluate the fidelity of clinician behavior to the intended intervention
- Learn about parents perspectives about communication challenge
- Learn about parental acceptability about parent-facing intervention elements including preparation for family meetings in the CICU and the written summary received after the family meeting

The following secondary endpoints will be used to assess CICU clinicians' perceived feasibility and acceptability with CST:

- Perceived acceptability of CST
- Metrics of enrollment rates and missing data
- Post-CST clinician survey
- Acceptability interview carried out with randomized subset of 8 intervention participants.

The following secondary endpoints will be used to assess CST impact on clinician behavior in simulated family meetings:

- Communication skill acquisition
- Team collaboration

The following secondary endpoints will be used to assess CICU clinicians' burnout rate and changes that CICU clinicians have implemented regarding family meetings due to the 2020 COVID-19 pandemic:

- Maslach burnout score¹⁰³
- COVID change in practice survey

The following secondary endpoints will be used to assess CST impact on clinician behavior in actual family meetings:

- Communication skill acquisition
- Team collaboration
- Team member perception and satisfaction with collaboration
- Fidelity of clinician behavior to intervention

The following secondary endpoints will be used to assess parents' perspectives about communication challenges in the CICU:

- Satisfaction feelings when communicating with the clinical team with decision-making
- Understanding of patient's medical condition
- Trust in medical team
- Levels of anxiety, depression, and post-traumatic stress

The following secondary endpoints will be used to assess parents' acceptability of the parent-facing elements of the intervention; including preparing for the meeting and their perception of the written summary after the family meeting

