After the consent process, clinicians will go through the interprofessional CST. The CST will occur over the course of 10 hours and will include short didactic sessions around giving bad news, eliciting parental goals, the core competencies of interprofessional collaborative practice⁸⁸, and adaptation for the CICU of the common components of a family meeting as represented in the CHOP Family Meeting Resources (http://intranet.chop.edu/sites/social_work/family-meeting-resources.html). Skills practice groups will include no more than 6 learners at a time. Didactic sessions may be in person or may be performed independently online as needed. Whether in-person or online, sessions may be audio or video recorded. There will be an online survey immediately after the CST to evaluate the clinicians' perception of effectiveness of the course. One month after the completion of the CST, a random sample of 8 participants will take part in a 15-30 minute acceptability interview regarding the CST.

Following the CST, a set of at least 23 actual family meeting encounters with trained clinicians will be audio recorded and coded.

A measure of team function will be assessed pre and post-CST by comparing the amount of time different members of the clinical team speak, and the kind of input offered by members of different disciplines within the team for simulated and actual family meetings. Team member perception and satisfaction with collaboration will be measured after their participation in clinical encounters both pre and post-CST by administering the modified Baggs CSACD-N tool to all clinician team members who participate in an actual encounter. This tool will capture each discipline's experience with collaboration with other team members and satisfaction with care decisions. Finally, fidelity of clinician behavior to the intended intervention in post-intervention family meetings will be determined by a fidelity checklist.

Actual meetings will each last 30-120 minutes. Clinicians participating in the intervention will be enrolled for the entirety of the study, lasting up to four years. They will have at least 21 points of contact with the research team, but some clinicians may participate more frequently due to the unknown composition of the observed actual family meetings.

Clinicians Not Participating in Intervention

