5 STUDY EVALUATIONS AND MEASUREMENTS

5.1 Screening and Monitoring Evaluations and Measurements

5.1.1 Evaluations, Measures

Measures for Co-Design

- Follow-Up focus group (See Appendix 11.5 for focus group guide)
- Post-focus group survey (See Appendix 11.6 for survey)
 - *Demographics of co-design participants*: The following baseline data will be collected: role in the co-design, gender, race, and ethnicity.
 - *Perception of co-design process and level of engagement*: Modified version of “Coalition Effectiveness Inventory”¹¹⁰⁻¹¹² that consists of one 14-item section measuring participants’ perceptions of the Co-design leader’s effectiveness and one 10-item section measuring participants’ perceptions of their own involvement and commitment to the Co-design process.

Measures for Post-Intervention

- *Course Evaluation - Satisfaction with CST and perception of skill usefulness*: This course evaluation is designed to determine clinicians’ perception of usefulness and satisfaction with the CST program. They will be asked to rate their level of agreement with aspects of the course on a 5 point Likert-type scale. Furthermore, the current burnout rate of clinicians will be assessed using the Maslach burnout score.¹⁰³ Additionally, changes that CICU clinicians have implemented regarding family meetings due to the 2020 COVID-19 pandemic will be recorded. Finally, clinician demographics will be collected including role in CICU, gender, race, and ethnicity. See Appendix 11.11 for complete course evaluation, Maslach burnout score, and COVID Change in Practice survey
- *Intervention fidelity checklist*: The Fidelity Checklist is a list of 7 behaviors of clinicians used to determine if clinicians used the tools and documents taught in the intervention. See Appendix 11.12 for the Intervention Fidelity Checklist
- *Acceptability Interview - 1 month follow-up*: We will do a semi-structured interview with clinicians reviewing their experience of the intervention process including what worked well and what they would recommend changing. Emphasis will be placed on virtual aspects of the training given the novelty of the implementation due to the COVID-19 pandemic. The semi-structured interview guide is in Appendix 11.13

Surveys for Clinicians Participating in Actual Family Meetings

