The following secondary endpoints will be used to assess clinician burnout and changes in communication in family meetings during COVID-19 pandemic

- The Maslach burnout scale, which uses Likert-type scales to measure aspects of burnout syndrome, including emotional exhaustion, depersonalization, and decreases in feelings of accomplishment.^{103,127}
- COVID-19 impact on communication in family meetings is a novel tool with 18 questions measuring the modality of communication with families and colleagues prior to during COVID-19 pandemic.

The following secondary endpoints will be used to assess CST impact on clinician behavior only in actual family meetings:

- *Modified Baggs CSACD-N tool*^{94,128}: The Baggs CSACD-N tool will measure team member perception and satisfaction with collaboration both pre and post-CST and will be given to all participating clinician team members. This tool will capture each discipline's experience with collaboration with other team members and satisfaction with care decisions. The difference in team member perception of collaboration will be measured using the CSACD-N pre and post-CST training. Means and standard deviations will be calculated for the tool and t-tests will determine if there are significant differences for each discipline pre and post-CST.
- Qualitative thematic analysis of family meetings that will identify if there are differences in themes prior to and after CST

The fidelity of the intervention implementation will be assessed by a Fidelity Checklist.

- The fidelity checklist will be scored by a study team member while reviewing the family meeting recording and reviewing information in Epic and parental survey responses. A summary score will be calculated for each family meeting conducted and descriptive statistics will be calculated for the post-intervention family meetings.

The following secondary endpoints will be used to assess parents' perspectives about communication challenges in the CICU when talking with the clinical team:

- In-person interviews prior to the intervention: These interviews will assess parents' experiences in communicating in the CICU with the clinical team. A constructivist grounded theory approach will guide qualitative analysis of interview transcripts.

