## Statistical Analysis Plan

Aim 2: Pilot test the co-design-adapted CICU TALC with CICU parents and clinicians to determine:

a) Acceptability of intervention: Hypothesis: Respondents will endorse above a critical threshold of acceptability on satisfaction instruments to 20 clinicians and 23 parents and in semi-structured interviews.

Analytic plan: A constructivist grounded theory approach will guide qualitative analysis of interview transcripts regarding acceptability of the intervention. Descriptive statistics will be calculated for quantitative data from the acceptability survey.

b) Feasibility of enrollment and data collection, and fidelity: Hypothesis: Feasibility will be defined by: i) 30% parental and 50% clinician enrollment and consent rates, and 80% subject retention, and attrition; ii) ability to collect outcomes data from 46 patients (CICU length of stay), from 46 parents and from 50% of eligible team members. and iii) intervention fidelity with 95% of enrolled parents and clinicians receiving parent-directed and team-directed interventions.

Analytic Plan: Data completeness and accuracy will be monitored. I will calculate descriptive summaries including means and standard deviations for continuous variables, and proportions for categorical variables. As appropriate for pilot trials, analyses will focus on estimating proportions of binary feasibility and fidelity endpoints and constructing 95% CIs. Analyses of parent-reported outcomes will primarily be descriptive. Means and standard deviations along with 95% confidence intervals will be calculated.

c) Impact of CICU TALC on CICU parent and team behavior in family meetings. Hypothesis: the intervention will increase parent speaking time by 60%, elicitation of parental concerns to 40%, and response to parental emotion by 30%. I will audio record 230 CICU family meetings occurring before CICU TALC is initiated and 230 after initiation and use quantitative methods to measure pre-vs-post differences in a) speaking time of parents and physicians; b) elicitation of parental concerns; and c) response to parental emotion.

Analytic Plan:

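### The SAP judges intervention fidelity by who received the intervention and leaves out the protocol's checklist of clinician behaviour in meetings

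*SAP*

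**What the plan says.** **SAP, Aim 2b.** Feasibility is defined by several targets, one of which is "intervention fidelity with 95% of enrolled parents and clinicians receiving parent-directed and team-directed interventions". The analysis is described as "estimating proportions of binary feasibility and fidelity endpoints and constructing 95% CIs". Neither 'enrolled' nor 'receiving' is defined, and the checklist is not named anywhere in the SAP.

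**Protocol.** Section 2.2 lists as a secondary objective: "Evaluate the fidelity of clinician behavior to the intended intervention". Section 3.1 says how this is to be done: "fidelity of clinician behavior to the intended intervention in post-intervention family meetings will be determined by a fidelity checklist". Section 5.1.1 describes the instrument: "The Fidelity Checklist is a list of 7 behaviors of clinicians used to determine if clinicians used the tools". Section 5.2.1 applies it to every recorded post-intervention meeting. Under section 6.2 a study team member scores it while "reviewing the family meeting recording and reviewing information in Epic and parental survey responses"; each meeting gets a summary score, and the post-intervention scores are described without a pass mark.

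**Condition on enrolment.** Section 3.1.4 requires clinicians in the intervention group to finish every part of the CST if they are to remain in the study.

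**The concern.** The two documents use one word, fidelity, for two quantities. The SAP asks whether people were given the intervention. The protocol asks whether clinicians then did what the intervention intends when they met families.

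The first is necessary for the second but does not imply it. A trained clinician may run a meeting exactly as before. If the fidelity conclusion rests on receipt alone, the pilot can report that its fidelity hypothesis was met without having addressed its own fidelity objective. Protocol 6.4 describes this study as a pilot for a future stepped wedge study. Its designers will want to know whether training changes conduct in the room; a receipt figure tells them only that training took place.

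**Working it through.** The 95% is a chosen threshold with no calculation behind it, so there is no figure to reproduce. The check has three steps.

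**1. The two definitions side by side**

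| | SAP Aim 2b | Protocol 2.2, 3.1, 5.1.1, 5.2.1, 6.2 |
|---|---|---|
| Construct | Receipt of the intervention | Clinician behaviour |
| Unit | Person (parent or clinician) | Recorded post-intervention meeting |
| Scale | Binary proportion with 95% CI | Summary score from 7 behaviours |
| Threshold | 95% | None |

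They differ in every row, so a result on one cannot stand in for a result on the other.

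**2. What the clinician half can show**

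Inputs: at least 20 intervention clinicians (Protocol 3.3.2; the SAP also uses 20), and the completion rule in Protocol 3.1.4. Assumption: receiving means completing CST.

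Let c be the clinicians who complete CST and r those removed for not completing it.

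- Denominator of clinicians who remain enrolled: receipt = c/c = 100% for any c. With c = 20, the exact (Clopper-Pearson) lower limit is 0.025^(1/20) = 0.832, giving a 95% CI of 83.2% to 100%. The result is the same whether meetings score 0/7 or 7/7 on the checklist.
- Denominator of all clinicians who consented to CST: receipt = c/(c + r). The criterion needs c/(c + r) ≥ 0.95, that is r ≤ c/19. With c = 20, r ≤ 1.05. One removal gives 20/21 = 95.2%, which passes. Two give 20/22 = 90.9%, which fails.

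The choice of denominator therefore decides whether the clinician half can fail at all. Even when it can, it measures completion of training and not conduct in meetings. The values of r are illustrative; the documents give no expected number of removals.

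**3. What the threshold requires in the groups assigned to the intervention**

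The count needed is 0.95 × n, rounded up, with exact 95% limits.

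| Group | n | Needed | Proportion | 95% CI |
|---|---|---|---|---|
| Clinicians (SAP, Protocol 3.3.2) | 20 | 19 | 95.0% | 75.1% to 99.9% |
| Parents (SAP Aim 2a) | 23 | 22 | 95.7% | 78.1% to 99.9% |
| Evaluable post-intervention dyads (Protocol 3.1) | 30 | 29 | 96.7% | 82.8% to 99.9% |
| Maximum post-intervention dyads (Protocol 3.1) | 50 | 48 | 96.0% | 86.3% to 99.5% |

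The parent rows can fail. The parent-directed elements are preparation for the meeting and a written summary afterwards (Abstract; Protocol 1.2), and parents are asked whether they were given the preparation worksheet and whether clinicians followed it up (Protocol 5.1.1).

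**The case against.** The best defence is that behavioural fidelity is already planned. The protocol scores the checklist for every recorded post-intervention meeting and describes the scores, so poor adherence would be visible, and silence in the SAP does not cancel a protocol endpoint. That stands, and it limits the harm. It does not close the gap: neither document says how the checklist bears on whether the fidelity hypothesis was met.

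A second defence is that receipt is a legitimate part of fidelity. The protocol itself files the parents' use and acceptability survey under fidelity of parent preparation (5.1.1, 6.2). That also stands, and it is a reason to keep the receipt figure alongside the behavioural one.

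Four stronger readings are tempting, and the documents do not support them.

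- A reader might infer that the criterion would be met even if nobody used any of the tools. It would not: if worksheets and summaries did not reach parents, the parent half would fail. The gap concerns clinician conduct that parents do not receive as a document.
- A reader might count everyone enrolled, including observed clinicians who are never trained and pre-intervention dyads, and conclude that 95% is unattainable. That is an implausible reading. Aim 2 concerns the piloted intervention and gives its acceptability numbers as "on satisfaction instruments to 20 clinicians and 23 parents", and the untrained clinicians belong to a cohort defined as not taking part in it. The sound point is only that the denominator should be stated.
- A reader might treat the 95% as a rule for proceeding to the main study. The SAP presents it within a hypothesis that defines feasibility and attaches no progression rule.
- A reader might suppose that missing parent surveys must pull checklist scores down. The checklist appendix is not in the supplied text, no rule scores a missing item as zero, and the recording or Epic may supply the information. What can be said is that no rule for unscorable items is given.

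**Conclusion.** The point holds. The SAP's fidelity criterion measures receipt, the protocol's objective is behaviour, and the planned behavioural measure has no role in the SAP's fidelity conclusion.

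The size is best stated in two parts. If receiving means CST completion and the denominator is clinicians still enrolled, the clinician half is met almost by construction and carries no information about meetings. Both conditions are assumptions, since the SAP defines neither term. The parent half is informative about delivery of the worksheet and summary, and may overlap with checklist items; the overlap cannot be checked without the appendix. The mismatch of construct, unit and scale depends on none of these assumptions.

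This should be corrected. It affects the answer to one stated secondary objective and does not undermine the other endpoints.

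**What to change.** Amend SAP Aim 2b as follows.

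- **Receipt (reach).** Keep the 95% figure, and define receiving separately for clinicians and for parents. State the denominators: all clinicians who consented to CST, including any later removed for not completing it, and all post-intervention dyads.
- **Behavioural fidelity.** Add checklist adherence in recorded post-intervention meetings. Report the per-meeting summary score and the percentage of meetings showing each behaviour, with 95% CIs. Base the fidelity conclusion on receipt and adherence together. Do not carry the 95% threshold over to the checklist, because nothing in the documents supports that value for behaviour scores.
- **Unscorable items.** Report how many items could not be scored for lack of source data. Show results with those items excluded and with them counted as not performed. Exclusion alone could flatter adherence if families who did not return the survey were also less often prepared.

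The cost is SAP text and a little more analysis. The checklist is already planned for every recorded post-intervention meeting, so no data collection is added. The fidelity statement may be less favourable than one based on receipt alone.

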Potential subjects will be screened using the protocol inclusion and exclusion criteria. Parent-patient dyads will be recruited into the study in person, over the phone, or via e-mail. The goal for enrollment will be up to 50 parent-patient dyads, with 30 evaluable parent-patient dyads. Parent-patient dyads who are enrolled in the post-intervention follow-up phase will be asked for access to information entered into the REDCap based Family Meeting Worksheet if they choose to use it, will be given an online survey in person or via e-mail to obtain post-intervention data assessing parental satisfaction, understanding, trust in the clinical team, emotional well-being and parents' acceptability of the parent-facing elements of the intervention, which includes preparation for the meeting and their perception of the written summary after the family meeting. Medical record review of this group of parents will utilize EPIC and the PC⁴ database, but will not require patient or parent involvement. A subset of enrolled patient-parent dyads will also be invited to participate in an interview assessing parents' acceptability of the parent-facing elements of the intervention.

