3.1.3 Pre-CST Intervention Phase

Clinicians Not Participating in Intervention: Consented clinicians not participating in the intervention will be audio recorded in their previously scheduled family meetings. Clinicians not participating in the intervention will complete an online survey after the actual family meeting that they are observed participating in.

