3.1.5 Follow-Up Phase

Clinicians Participating in Intervention: After CST, a set of actual family meeting encounters with these trained clinicians will be audio recorded and coded, ensuring there are 23 meetings with each category of person trained. We estimate a total of 28 meetings will need to be recorded in order to obtain 23 meetings with each discipline. Clinicians participating in the intervention will complete an online survey after the actual family meeting that they are observed participating in.

This survey will measure team member perception and satisfaction with collaboration. We will administer the modified Baggs CSACD-N tool to all clinician team members who participate in an actual encounter, which will capture each discipline's experience with collaboration with other team members and satisfaction with care decisions.

Clinicians Not Participating in Intervention: Consented non-participating clinicians will have their normal, scheduled family meetings. Actual family meeting encounters with these clinicians will be audio or video recorded and coded. Clinicians not participating in the intervention will complete the same online survey as those clinicians participating in the intervention after the observed actual family meeting.

Parent-patient Dyads Participating in the Survey or Interview After Intervention: Potential subjects will be screened using the protocol inclusion and exclusion criteria. Parent-patient dyads will be recruited into the study in person, over the phone, or via e-mail. The goal for enrollment will be up to 50 parent-patient dyads, with 30 evaluable parent-

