3.3.2 Total Number of Study Sites/Total Number of Subjects Projected

The study will be conducted within the Children's Hospital of Philadelphia. The co-design phase will be conducted with participants from units within the hospital and parents with children who had previously been hospitalized at CHOP, and the intervention and evaluation of the intervention will occur exclusively in the CICU at CHOP.

For clinicians participating in the co-design, approximately 15 clinician staff will be enrolled and 5 parents will be enrolled.

For clinician subjects participating in the intervention, recruitment will stop when at least 20 CICU clinicians are enrolled.

For non-participating clinicians, recruitment will stop when we obtain at least 56 family meetings per discipline of participating clinician team member.

We estimate that approximately 300 clinicians who are not participating in the intervention may be observed subjects in the actual meetings.

For parent-patient dyads participating prior to the intervention, recruitment will stop when 100 evaluable parent-patient dyads are enrolled for the survey and 30 evaluable parent-patient dyads are enrolled for the interview.

For parent-patient dyads participating after the intervention, recruitment will stop when up to 30 evaluable parent-patient dyads are enrolled for the survey and a subset of up to 15 parent-patient dyads will be asked to participate in the interview.

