6.4 Sample Size and Power

We hypothesize that the CST will change clinician behavior by increasing the number of skills demonstrated in a simulated family meeting. Sample size calculations using existing data about acquisition of skills being evaluated in the CST²⁹ demonstrated that a total of 20

clinicians will be needed to identify significant changes in the following skill outcomes: discussing the big picture, responding to emotion, and performing several empathetic verbal skills using 80% power and an alpha=0.05.

Sample size calculations for determining change in clinician skill acquisition by discipline requires that there be an adequate number of actual encounters recorded such that they can be analyzed by provider type. Sample size calculations for simulated family meetings apply here as well in that we will need to have at least 20 team encounters pre and post-CST intervention to be able to look at the change in outcome before and after the intervention. Since there are generally at least 2 clinicians in each team encounter, we will examine the individual skill acquisition within each part of the team encounter. Within each discipline, there are several clinicians involved in multiple team meetings. We will use fixed-effects regression with a clinician identifier variable as a covariate so that we can examine the effect of CST intervention on skill acquisition, adjusting for the effects of individual clinicians.

Team function will be analyzed by comparing the change in the number of minutes that clinicians from each discipline speak in pre and post-CST meetings using linear regression and controlling for the length of the meetings. Sample size calculations based on previous data⁸⁷ and assuming 80% power and an alpha=0.05 will only require 3 paired respondents pre and post-CST to identify significant differences.

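### The SAP plans 230 recorded family meetings before and 230 after CICU TALC without a derivation, the protocol estimates 28 post-training recordings, and nothing reconciles the two

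*SAP*

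**What the plan says.** SAP Aim 2c: "I will audio record 230 CICU family meetings occurring before CICU TALC is initiated and 230 after initiation". The recordings support pre/post comparisons of speaking time, elicitation of parental concerns and response to parental emotion. The aim gives target effects but no baseline rate, standard deviation, power or clustering assumption from which 230 could follow.

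The protocol has several smaller figures:

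- Section 3.1.5 (post-training): "We estimate a total of 28 meetings will need to be recorded in order to obtain 23 meetings with each discipline".
- Section 3.1 (post-training): "a set of at least 23 actual family meeting encounters with trained clinicians will be audio recorded and coded".
- Section 6.4, extending a calculation made for simulated meetings: its results "apply here as well in that we will need to have at least 20 team encounters pre and post-CST intervention". The underlying calculation was for 20 people: that many "clinicians will be needed to identify significant changes in the following skill outcomes".
- Section 3.1.3 (pre-training) gives no count: "Consented clinicians not participating in the intervention will be audio recorded in their previously scheduled family meetings".
- Section 3.3.2, for non-participating clinicians: "recruitment will stop when we obtain at least 56 family meetings per discipline of participating clinician team member".

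On post-intervention families, section 3.1 says: "The goal for enrollment will be up to 50 parent-patient dyads, with 30 evaluable parent-patient dyads". Table 1 and section 4.5.5 schedule one recording visit for each such dyad.

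**The concern.** The number of recorded meetings is the sample size for Aim 2c, which holds the SAP's pre/post tests; Aims 2a and 2b are descriptive or estimate proportions. A reader of the SAP would expect estimates based on 230 meetings per period. A reader of the protocol would expect roughly a tenth to an eighth of that after training, and would find no planned pre-training count beyond the minimum of 20.

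Three things depend on the answer: how precise the comparisons will be, when recording is complete, and which analyses are run. On the last, the SAP makes its mixed models, and so its adjustment for repeated participants, conditional on sample size.

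**Working it through.** **1. Can 230 be reproduced?** No. Neither document supplies inputs for it. The only absolute target in Aim 2c is elicitation reaching 40%. Solving backwards (two-sided 0.05, 80% power, no continuity correction), 230 per period results only if a baseline of about 27.5% to 27.8% is assumed, and neither document states one.

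**2. Do the protocol's figures agree with each other?** For the post-training recordings, yes. Twenty-eight recordings meet at least 20, at least 23, and 23 with each discipline.

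**3. Do they agree with the SAP?** 230 / 28 = 8.2, and 230 / 23 = 10 exactly. The 20 and 23 are minimums, which 230 does not breach. The 28 is an estimate of the total needed, and 230 cannot be squared with it.

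**4. Could the post-phase families supply 230?** With at most 50 enrolled dyads, 230 / 50 = 4.6 recordings per dyad at the least, against one scheduled recording visit. No such ratio can be formed for the pre phase, because section 8.6.1 selects those meetings from scheduled family meetings and Table 1 ties no recording to the pre-intervention dyads.

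**5. What does the difference do to precision?** Assumptions: meeting-level analysis, independent meetings, equal numbers per period, two-sided 0.05 (protocol section 6.3.2). The 20% versus 40% contrast is illustrative: 40% is the SAP's target and 20% is assumed. The 80% power is borrowed from protocol section 6.4; the SAP sets none for this aim.

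Half-width = 1.96 × √[(0.2×0.8 + 0.4×0.6)/n] = 1.96 × √(0.40/n). The detectable standardised difference d is from the noncentral t distribution.

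| Meetings per period | 95% CI half-width | Detectable d, 80% power | Interval width relative to 230 |
|---|---|---|---|
| 23 | 1.96 × √(0.40/23) = 0.258 | 0.84 | √(230/23) = 3.16 |
| 28 | 1.96 × √(0.40/28) = 0.234 | 0.76 | √(230/28) = 2.87 |
| 230 | 1.96 × √(0.40/230) = 0.082 | 0.26 | 1 |

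**6. The figure of 56.** 2 × 28 = 56, so 56 would fit a total of recordings if 28 were also made before training. That is an inference, since no pre-training estimate is given. The section's wording makes it a count per discipline and does not say how it was reached.

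**The case against.** **The protocol's minimums set no cap, and families can meet more than once.** True for 20, 23 and 56, and 4.6 recordings per dyad is implausible rather than impossible. Neither removes the clash with an estimated total of 28.

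**230 is simply a slip for 23.** This is plausible. It is exactly ten times 23, Aim 2 also uses 23 parents and 46 (2 × 23) patients and parents, and protocol section 3.1 uses 23 meetings. The documents cannot prove it. If it is so, the SAP figure is wrong by a factor of ten and still needs correcting.

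**This is a pilot and the comparison is secondary.** That stands. It limits the consequence but does not make the two counts compatible.

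Some stronger readings are tempting but unsupported:

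- A reader might infer that 56 per discipline contradicts a target of 46 (2 × 23). The target of 23 per discipline is set only after training, and 56 is itself a minimum. The figure is unexplained, not shown to be in conflict.
- A reader might divide 230 by the 30 evaluable dyads to get 7.7 recordings each. Sections 3.3.2 and 8.5 define those 30 as evaluable for the survey, so enrolled dyads are the right denominator.
- A reader might infer that 23 to 28 meetings are too few. That depends on an unstated baseline. By exact enumeration of the chi-square test, power to detect a rise to 40% at 23 / 28 per period is 88% / 93% from an assumed 5%, but 32% / 38% from an assumed 20%.

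**Conclusion.** The two documents disagree about eightfold on the number of post-training recordings for Aim 2c, the SAP's figure has no derivation, and no text reconciles them. The pre-training figure of 230 is equally unsupported; the protocol's only pre-training number is a minimum of 20, carried over from a calculation for clinicians in simulated meetings.

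If the protocol's counts are being run, 95% intervals are about three times as wide as the SAP implies. This rests on independent meetings, equal periods and the assumed 20% versus 40%. Protocol sections 6.3.2 and 6.4 and the SAP all expect clinicians to recur across meetings. That would change the figures and could make them optimistic.

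The disagreement is certain; which number was intended is not. It must be resolved because it is the sample size of the SAP's comparative analysis, although the primary endpoint (section 6.1) is qualitative and unaffected. The figure of 56 needs clarifying, no more.

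**What to change.** The sponsor should confirm one pre-training and one post-training count, checking first whether 230 was meant to be 23.

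**If the protocol's design is the one being run:**

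1. In SAP Aim 2c, replace both 230s with the confirmed counts: 23 per period, or about 28 after training to obtain 23 with each discipline, together with an explicit pre-training number.
2. State the same pre-training number in protocol section 3.1.3. The minimum of 20 in section 6.4 should not be adopted by default, given where it came from.
3. Reword section 3.3.2 to say whether 56 is a total of recordings or a count per discipline.
4. Add to Aim 2c the one precision figure that matches the confirmed count. Model wording for 28 per period: *With 28 recorded meetings per period, treated as independent, the 95% confidence interval for a difference between an assumed 20% and 40% has a half-width of about 23 percentage points; clinicians who appear in several meetings would change this figure and could make it optimistic.* At 23 per period the half-width is about 26 points. Recalculate if the periods are unequal.

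**If 230 per period is intended:** give its derivation (baseline, effect, alpha, power, allowance for recurring clinicians) and revise protocol sections 3.1, 3.1.5, 3.3.2 and 6.4 to match.

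**Cost:** wording only in the first case, with a less favourable stated precision. In the second, the protocol's recording plan has to change.
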